4. Visuospatial priming: The subject's task is to press one of four computer keys, which correspond spatially to four loci on a PC screen. Each trial includes two successive displays, each consisting of a brief

presentation of an 'X' and an 'O' in two of the four locations. On each presentation, subjects press the key corresponding to the location of the target letter 'O' while ignoring the distractor letter 'X'. The 'X' and 'O' within each display are visible for 150 msec; the time between displays is 350 msec. The task consists of 50 display pairs. There is a baseline condition in which the positions of the target ('O') and non-target ('X') in the probe display are unrelated to their positions in the prime display. In "repetition priming" (the facilitation condition) the position of the target remains the same on the successive displays. In "negative priming" (the inhibition condition) the target in the probe display appears in the location where the non-target had previously been.

5. Latent Inhibition: A computerized visual latent inhibition task is used. Subjects are pre-exposed or nonpreexposed to a visual stimulus (pattern on a computer screen) that will, in the subsequent phase of the testing, have predictive value. Using the computer keyboard for responding the subjects will predict computer screen changes, being influenced by the earlier exposure parameter. Each phase requires 5 minutes time to run. Preexposed control subjects require more trials prior to reaching a criterion score on their predictive response.

Pregnancy test: The pregnancy test is able to detect tiny amounts of the pregnancy hormone hCG (Human Chorionic Gonadotropin) in urine. This hormone is produced in increasing amounts during the first part of pregnancy. HCG will be measured by a urine "dip-stick" ("Surecheck Early Pregnancy Test"). This test is a midstream format test for the detection of the pregnancy hormone in urine.

j. Statistics: Tests for homogeneity of variance are performed, and if appropriate, analyses of variance (ANOVA) used. Statview/Superanova software is used on the Macintosh. For startle data, P-Alone amplitude, PPI and startle latency are analyzed by ANOVAs; for drug studies, drug dose is used as a within-subject factor. Habituation is detected by a significant effect of trial block. Visuospatial priming is analyzed separately for baseline, facilitation, and inhibition conditions using ANOVAs. Baseline is a measure of visuospatial response time, while facilitation and inhibition scores are measures of sensorimotor modulation. Nonparametric statistics are used for the Latent Inhibition analyses because data from this test tend toward a bimodal distribution. A rank sum factorial analysis is used for the data. Other dependent measures will be analyzed with parametric or non-parametric analyses, generally consisting of mixed design ANOVAs, as appropriate. Following a significant ANOVA, specific comparisons are made using Tukey's tests. Alpha is 0.05.

Power considerations: Sample sizes vary across the different studies, based on issues ranging from the study design and goals to empirical evidence for effect sizes with the proposed drug or measure. For example, "ONE-DAY" studies are designed to identify and "pilot" optimal stimulus parameters for testing specific hypotheses, and these studies may not be powered to achieve traditional levels of statistical significance. On the other hand, designing studies of drug effects on PPI and related measures in control or patient populations requires detailed power information.

For example, to assess the effects of memantine on "gating" measures in schizophrenia patients, the primary measure will be evaluated by 2-way repeated-measure ANOVA of PPI with memantine dose and prepulse interval as within-subject factors. The hypothesis that memantine will increase PPI in schizophrenia patients will be confirmed by a significant effect of dose (active > PBO) or significant dose x interval (int) interaction and post-hoc comparisons at one or more prepulse intervals. Existing data (see above) provide a strong *a priori* prediction that the 120 ms prepulse interval will be most sensitive to PPI-enhancing effects of MEM. The effect size (d) for PPI-enhancement by 20 mg memantine in HCS was 0.91; with a similar "d" in patients, 30 patients/dose yields power of 0.92 to detect the predicted memantine effects; with maximum expected attrition (n=24), power is 0.85. Past findings also lead to the prediction that these MEM effects would be most robust in subjects exhibiting the lowest basal PPI levels (d=1.80). Using a median split of mean basal (screening) PPI levels, ANOVA as above will detect a significant interaction of memantine dose x basal PPI level, or dose x basal level x int, and significant post-hoc comparisons at one or more prepulse intervals (again, 120 ms being the strongest *a priori* candidate). Given the published "d" in control subjects, a comparable "d" in the proposed 12-15 "low PPI" patients/dose group would yield power >0.95 to detect the predicted memantine effects.

Lastly, based on the impact of basal PPI level and personality measures in controls, we hypothesize that a critical moderating factor underlying PPI memantine sensitivity is COMT Val158Met genotype; specifically, we predict that "Val/Val" individuals will be most sensitive to memantine-enhanced PPI. This will be tested in two ways: first, by ANOVA as above, with COMT status as a between-subject factor, and memantine dose and prepulse interval as within-subject factors. Significant genotype x dose or genotype x dose x int interactions, with appropriate post-hoc comparisons, would confirm the hypothesis. Estimating d=1.53, based on the mean "d" of two "COMT phenotypes" in controls - low basal PPI (d=1.80) and high "novelty seeking" personality (d=1.27) - the proposed 11 Val/Val and 7 Met/Met patients/dose group would yield power of 0.90 to detect genotype-sensitive memantine effects. It is possible that various factors (including a skewed distribution of allele frequencies, or substantial genotype effects on basal PPI levels) might preclude detection of a significant 2- or 3-way interaction. A secondary (albeit weaker) test of the hypothesis will utilize separate ANOVAs in Val/Val vs. Met/Met subgroups, with predicted PPI-enhancing effects of memantine in the Val/Val but not Met/Met subgroups. Previous reports also predict a significant main effect of genotype, with PPI levels following the Met/Met>Val/Met>Val/Val gradient. Logistic regressions might be used, with genotype coded to reflect "dose" of the Met allele (Val/Val=0, Val/Met=1, and Met/Met=2), to assess the distribution of the neurophysiological and neurocognitive measures. All analyses will be conducted independently for each dose group. If comparable effects are evident with 10 and 20 mg doses, dose groups may be pooled to increase power for exploratory analyses (e.g. to detect genotype x drug effects).

Main effects of memantine on WM will be tested by one-way ANOVA with memantine dose as a withinfactor. Based on d=0.73 for increased WM after 20 mg MEM in controls (see above), the proposed 30 patients/dose group would yield power of 0.79 to detect significant WM-enhancing effects. While preliminary data yield less robust predictions for COMT subgroup sensitivities in memantine effects on WM performance, given the significant correlation of WM and PPI, and known impact of COMT genotype on PPI levels, we predict some differential (Val/Val > Met/Met) memantine sensitivity in this measure. If we estimate effects of COMT status on WM memantine-sensitivity to be comparable to those for PPI (65% increase in effect size), then the estimated d for Val/Val vs. Met/Met sensitivity should be 1.20, and the proposed genotype subgroup sizes would yield power of 0.65 to detect genotype-sensitive memantine effects on WM.

Secondary "biomarkers" are MMN and GBS. For MMN, positive memantine effects will be detected by increased MMN amplitude at electrode Fz. For GBS, positive memantine effects would be detected by increased 40 Hz evoked power at electrode Fz. Unlike those for PPI, predictions of positive memantine effects on MMN and GBS are not based directly on previous findings from our laboratory, using measures identical to those proposed herein. However, based on reports in healthy subjects from other laboratories of memantine effects on MMN (d=0.87) and ketamine effects on GBS (d=0.69), the proposed 30 patients/dose group would yield power of 0.90 and 0.75, respectively, to detect positive memantine effects on these measures.

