9. RESEARCH DESIGN AND METHODS

GENERAL METHODS:

a) Study populations: Study subjects, ages 18-45, are recruited from the community. Two subject populations are recruited: clinically normal control subjects, and patients with schizophrenia. The patient populations and upper age limit of 45 are used only for studies with memantine, which is prescribed clinically in geriatric populations for the treatment of Alzheimer's Disease. For all other studies, the sample is limited to clinically normal controls and the upper age limit is 35.

b) We ask new participants whether they would allow us to contact them regarding future studies. If they agree, our plan is to contact them at a future date for appropriate IRB approved studies.

c) For all drug evaluation studies, normal control subjects are recruited and screened for evidence of physical or psychological impairment; schizophrenia patients are recruited and screened only for

participation in drug evaluation studies with memantine. Each recruited subject is given a complete physical and psychiatric examination including medical, psychiatric, social and drug histories, an EKG and a urine test. For most studies, only male subjects, ages 18-35, are recruited. For a subset of studies, female subjects, and subjects up to age 45 will be recruited, as discussed below. All subjects are asked to arrange for transportation to and from any test session due to possible adverse effects for up to 12 hours after drug administration. During some or all of the tests the subject's performance may be monitored by the use of a non-recording camera. This is to ensure that the subject is awake and performing the task as instructed. Only the investigator running the test session will be able to see the subject, and this allows quantification of blink rate.

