d) Subject payment (also see below, section 18): For subjects participating in the "Within-Subject" test sessions, payment will be divided in the following schedule: on completion of screening day: \$30; on completion of first TEST SESSION day: \$100; On completion of second TEST SESSION day: \$130. This payment schedule provides appropriate incentive for the subjects to return for the second test day. This is to ensure that subjects return for the second and third test days. If subjects fail screening criteria for recreational drug use prior to any TEST SESSION day, they will not be tested further and will not be paid for that test day. We will recommend that subjects remain in our laboratory for monitoring until six and one half hours after pill ingestion. Should they choose to leave our facility for any reason prior to that time, it will be at their own risk. Their involvement in the study will be completed and payment on the Test Session day will be prorated to \$16 per hour.

e) Venopuncture: Venopuncture for COMT allelic testing in some subjects will occur during the initial visit, before or after what normally is titled the SCREENING SESSION in the studies listed below. A single venopuncture performed by certified individuals within the UCSD Medical Center GCRC/CTRI or Blood Drawing Station will be used to 10 cc of blood for COMT allelic testing. Based on specific needs of the experimental design (e.g. equal number of Met/Met, Val/Met and Val/Val allelic carriers, or subgroups of "high" vs. "low" PPI levels, based on the upper vs. lower quartile of a normal population distribution), subjects may be asked to come back for further testing, if they indicate they would like to do so. If participants continue to the remainder of the study, there will be 2 test days, one of which will involve placebo, and the other day involving an active dose of amphetamine (20 mg), memantine (20 mg) or other approved test drug/dose. The TEST SESSIONS will mimic those in the WITHIN-SUBJECT model below; however, venopuncture occurs only during the first visit.

f) Clinical assessment: Specific clinical assessment tools used in control and schizophrenia subjects are described in Section 10.

g) Test schedules:

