1. The "WITHIN-SUBJECT" study involves a single drug. There will be 2 test days – on the additional test day, subjects will receive either placebo or an active dose of one of the following: amphetamine (20 mg), memantine (10 mg) and memantine (20 mg). Some studies may require a venopuncture for genetic analysis as discussed above. A "model" example of a WITHIN-SUBJECT test schedule is shown below:

Test Day 1

0815-0845 Subject signs required forms, provides urine sample, eats standardized breakfast, venopuncture (if required)

0845-0900 Vital signs (VS) check, hearing and vision test, symptom rating scale.

0900-0915 drug or placebo administration.

0915-0930 VS check; symptom rating scales.

0930-0945 EMG electrodes applied.

0945-1000 VS check; symptom rating scales.

1000-1125 Startle response measurement, including PPI, habituation and intensity assessment.

1125-1140 VS check; symptom rating scales.

1140-1155 Visual LI or Visuospatial priming or MCCB

1155-1210 VS check; symptom rating scales.

1210-1300 Subject offered lunch from cafeteria.

1300-1600 VS check hourly; subject dismissed if VS within established parameters at 1600.

Test Day 2: 7-30 days after Test Day 1

0815-0845 Subject signs required forms, provides urine sample, eats standardized breakfast, venopuncture (if required)

0845-0900 Vital signs (VS) check, hearing and vision test, symptom rating scale.

- 0900-0915 drug mg or placebo administration: WHICHEVER DOSE WAS NOT RECEIVED ON TEST DAY 1
- 0915-0930 VS check; symptom rating scales.
- 0930-0945 EMG electrodes applied.
- 0945-1000 VS check; symptom rating scales.
- 1000-1125 Startle response measurement, including PPI, habituation and intensity assessment.
- 1125-1140 VS check; symptom rating scales.
- 1140-1155 Visual LI or Visuospatial priming or MCCB
- 1155-1210 VS check; symptom rating scales.
- 1210-1300 Subject offered lunch from cafeteria.
- 1300-1600 VS check hourly; subject dismissed if VS within established parameters at 1600.

Subjects will be instructed to not eat on the morning of the test, and instead will be served a standardized meal 30 min prior to drug administration, so as to maintain a controlled and consistent impact on drug absorption.

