The present protocol proposes the use of 10 and 20 mg memantine; our experience to date is limited to the higher of these two doses (20 mg); based on the published literature, we expect any potential AEs to be dose-dependent, and thus the 20 mg dose (vs. the 10 mg dose) represents the one with the highest likelihood of AEs, should any occur. In our published data (n=19), the only detectable impact of 20 mg memantine (other than those in our neurophysiological measures) were: 1) an increase in self-reported level of happiness 30–230 min after pill administration; and 2) a small decrease in spontaneous blink rate, an effect generally suggestive of reduced fatigue or somnolence. No significant changes in self-rated dizziness, queasiness or drowsiness were detected at any time after 20 mg memantine. Autonomic measures (heart rate, systolic or diastolic blood pressure) were also not significantly changed by memantine. Our unpublished data (n=8) with 20 mg memantine (see above), confirms all of these findings, including no significant change in autonomic measures or self-rated dizziness, queasiness or drowsines self-rated happiness and decreased blink rate. In addition, as described above, we noted a significant increase in working memory after memantine, as measured by the MCCB.

Memantine has been studied in schizophrenia patients. It is important to note that these studies involved daily dosing for many weeks or longer, while the present protocol proposes only a single active dose of memantine. Nonetheless, the findings are informative:

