For the drug evaluation study, the proposed drugs carry a very small risk of toxicity or adverse side effects in the doses to be used in this study. The most common side effects associated with each drug are listed in Section 8 above, and typically include nausea, somnolence and dizziness. We do not plan to administer these drugs to subjects in whom it is contraindicated, such as subjects with known cardiovascular or neurological disorders. The doses selected for use in these studies are in the low- or below-therapeutic range for these drugs when they are used clinically, and in most cases, the selected dose is equal to or less than the lowest recommended starting clinical dose for the drug. To address the potential for some of these drugs to produce changes in blood pressure, we will carefully monitor subjects' vital signs, and will not release subjects from the hospital until their vital signs are within normal limits. To address the possible side effect of somnolence, we will instruct subjects to arrange for their transportation from the hospital on test days. For studies that include women of childbearing potential, there is the possibility of unforeseen harm to an unborn child due to the administration of drugs. To address this risk, all female subjects will be asked to provide a urine sample to test for pregnancy and we will exclude participants who test positive. Additionally, all female subjects in these studies will be required to use a non-drug birth control method, such as abstinence, diaphragm, non-hormone intrauterine device to prevent pregnancy during the study. Subjects will be told to report if their menstrual cycle is inconsistent or if suspect that they are pregnant. Drugs will be dispensed by a licensed physician, and a licensed physician will be present on the premises at all times during testing. The consent forms include the related risks specific to the drug it refers to.

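### Structured symptom ratings end about 3 hours after dosing, no later adverse-event enquiry is scheduled, and the passages on leaving need to be reconciled

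*Protocol*

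**What the plan says.** Section 9.g of the Protocol gives one model schedule for both test days. Dosing is "0900-0915 drug or placebo administration". Symptom scales are listed once before the dose and four times after it, the last being "1155-1210 VS check; symptom rating scales". After lunch the schedule has "1300-1600 VS check hourly; subject dismissed if VS within established parameters at 1600".

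The text after the schedule in 9.g adds three things. Vital signs are taken lying, sitting and standing. Sessions stop for vomiting, severe discomfort or other unforeseen consequences. Dismissal requires heart rate and blood pressure within set ranges, no sign of dizziness and no significant postural change.

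Other sections bear on the same hours:

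- Section 9.c asks subjects to arrange transport "due to possible adverse effects for up to 12 hours after drug administration".
- Section 9.d: "We will recommend that subjects remain in our laboratory for monitoring until six and one half hours after pill ingestion". A subject may leave sooner on his or her own responsibility, which ends participation.
- Section 9.h lists dizziness, restlessness, nausea and headache as the common effects of memantine. For amphetamine it includes restlessness and dizziness.
- Section 14 adds somnolence, and says staff "will not release subjects from the hospital until their vital signs are within normal limits".
- Section 15 tells anyone who reports sedation at the end not to drive, and gives an after-hours contact route that the participant has to use.

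Test Day 2 is 7 to 30 days after Test Day 1. Its pre-dose procedures include vital signs and a symptom scale.

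**The concern.** Most of the side effects the Protocol names are felt rather than measured. Heart rate and blood pressure readings do not record nausea, headache or restlessness. If structured enquiry stops at about 3 hours while the Protocol itself allows for effects up to 12 hours, later symptoms enter the record only when a subject speaks up. A later statement that no adverse events occurred would then rest on systematic symptom data from about the first quarter of the window the Protocol names, plus spontaneous report.

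Two groups are most exposed. Subjects who leave early may do so because they feel unwell, and their participation ends there. Subjects returning for Test Day 2 may receive the second dose without anyone having asked what followed the first session. The several statements on leaving also make it unclear what was required of a subject before departure, and so what a complete test-day record should contain.

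**Working it through.** This is clock arithmetic on the model day, taken at both ends of the dosing slot. No sample size, power or alpha is involved.

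**Inputs.** From 9.g: dose 0900-0915, last scale 1155-1210, last listed vital-sign check and dismissal 1600. From 9.c: a 12-hour window. From 9.d: a recommended stay of 6.5 h.

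**1. The plan's own 6.5 h against the 1600 dismissal.**
- 0900 + 6 h 30 = 1530, and 0915 + 6 h 30 = 1545.
- 1600 − 0900 = 7 h 00, and 1600 − 0915 = 6 h 45.
- The recommended stay ends 15 to 30 min before the dismissal check. A 1600 dismissal satisfies the recommendation. A subject leaving between 1530/1545 and 1600 meets 9.d but has not reached the check in 9.g.

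**2. Last structured rating.**
- 0900 dose: 1155 − 0900 = 175 min and 1210 − 0900 = 190 min.
- 0915 dose: 1155 − 0915 = 160 min and 1210 − 0915 = 175 min.
- Range 160 to 190 min. As a share of 12 h: 160/720 = 22% to 190/720 = 26%.

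**3. What remains of the 12-hour window.**
- The window ends at 0900 + 12 h = 2100, or 0915 + 12 h = 2115.
- After a 1600 dismissal: 5.0 h (5.0/12 = 42%) to 5.25 h (5.25/12 = 44%).
- After 1210: 8 h 50 min to 9 h 05 min with no scheduled rating scale.

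**4. If the timetable slips.** The cognitive battery (MCCB) is one option for a 15-minute slot, but section 9.i says it takes about 1 hour. Assume it takes the hour and later items move back 45 min. The last rating then falls at 205 to 235 min (3.4 to 3.9 h). Assume also that the 60 minutes of EEG come before it: 265 to 295 min (4.4 to 4.9 h). Neither case comes near 12 h.

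**5. What is asked after 1210, symptom by symptom.**

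| Symptom named | Scheduled enquiry after 1210 |
|---|---|
| Dizziness | Checked at dismissal (9.g); no rating listed |
| Sedation, somnolence | Acted on if reported (section 15); no rating listed |
| Nausea | None scheduled; vomiting stops the session (9.g) |
| Headache | None scheduled; severe discomfort stops the session (9.g) |
| Restlessness | None scheduled; severe discomfort stops the session (9.g) |

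**6. Leaving, side by side.**

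| Place | Statement |
|---|---|
| 9.d | Stay of 6.5 h recommended; earlier departure allowed on the subject's own responsibility |
| 9.g, schedule | Dismissal at 1600 on vital signs |
| 9.g, text after schedule | Same times; adds dizziness and postural criteria |
| Section 14 | No release until vital signs are normal |

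**The case against.** The strongest reply is that safety observation does not stop at 1210. A licensed physician is on the premises during testing. Sessions stop for vomiting or severe discomfort, dizziness and postural change are checked at dismissal, and reported sedation is acted on. All of this stands. A reader might infer that delayed dizziness or sedation would simply go unnoticed while the subject is on site; the Protocol does not support that. What is missing between 1210 and 1600 is a structured symptom record.

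Other stronger readings also fail:

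- *That the Protocol expects effects for 12 hours.* Section 9.c calls them possible and uses them as a reason to arrange transport.
- *That nothing can be collected after 1600.* Dismissal is conditional, so a subject outside the ranges would stay, although no further schedule is given for that case.
- *That the passages give contradictory leaving times.* A 1600 dismissal meets the 6.5 h recommendation, the text after the schedule adopts the same times, and section 14 gives a condition rather than a time. The difference is mainly about conditions. Section 9.d can be read as voluntary departure and section 14 as release by staff, but neither says so.
- *That the laboratory's own data show late adverse effects.* Section 9.h reports "an increase in self-reported level of happiness 30–230 min after pill administration". This extends to 1250-1305 on the model day, 40 to 55 min after the last rating slot ends. But it is raised happiness, and the same section reports no significant change in dizziness, queasiness or drowsiness at any time after 20 mg memantine.

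Two further points stand in part. The schedule is labelled a model, so its times are illustrative; but it is the only dosing-day timetable given, and step 4 shows that slippage does not close the gap. Test Day 2 does have a pre-dose symptom scale, and section 11 repeats control screening at testing. Neither is described as asking about the interval since Test Day 1. Consent pages are not in the public document, so take-home instructions may exist that cannot be seen here.

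**Conclusion.** The point holds in a limited form. In the model day, structured symptom ratings end 160 to 190 min after dosing. Nausea, headache and restlessness have no scheduled rating after 1210. Nothing is scheduled for the 5.0 to 5.25 h of the Protocol's 12-hour window that follow a 1600 dismissal, and no question about events since Test Day 1 is listed before the second dose. Later effects reach the record only by spontaneous report.

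This concerns completeness of adverse-event recording after single doses. It does not touch the SAP's hypotheses on prepulse inhibition, mismatch negativity or the auditory steady-state response, none of which uses late ratings. It does not show that harm was missed. It rests on two assumptions: that actual sessions followed the model day reasonably closely, and that no follow-up is set out in material outside the public text.

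Sections 9.d, 9.g and 14 also need reconciling on when and under what conditions a subject leaves. Which rule applies is for the sponsor.

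**What to change.** 1. Repeat the existing symptom rating scales at the hourly 1300-1600 vital-sign checks on both test days.
2. Add an adverse-event question covering the period since Test Day 1 to the Test Day 2 pre-dose procedures.
3. Record any early departure, with its reason, as a safety observation.
4. Optionally, add a brief contact after Test Day 2 and after any early departure. Neither is reached by the question in item 2.
5. Reconcile 9.d, both parts of 9.g and section 14 into one statement on leaving, with the content left to the sponsor.

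The cost is a few minutes of self-rating while subjects are already on site, slightly more data entry and more minor adverse events reported. Item 4, if adopted, adds one short call. For sessions already completed, the safety report can state that structured symptom data end about 3 hours after dosing and that later events were recorded by spontaneous report.

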Statistical Analysis Plan Memantine Effects on Sensorimotor Gating and Neurocognition in Schizophrenia NCT03860597 R01MH094320 Latest IRB approval date: June 21, 2022 IRB expiration date: July 7, 2023

The primary statistical considerations for these data are those required to test the primary hypothesis that memantine (MEM) would enhance sensorimotor gating and related measures of auditory information processing in schizophrenia (SZ) patients. The operational measure of sensorimotor gating was prepulse inhibition of startle (PPI). The primary hypothesis was tested by a 2-way repeated-measure ANOVA of PPI with MEM dose and prepulse interval (10, 20, 30, 60 or 120 ms) as within subject factors. The key dependent measure was %PPI, calculated according to common practices in the literature. The hypothesis that MEM will increase PPI in SZ patients was to be confirmed by a significant main effect of drug (active > PBO) or significant interaction among the variables of drug, dose (10 or 20 mg), diagnosis (healthy subject (HS) or SZ) or prepulse interval, and informative post-hoc comparisons. The assumptions behind these analyses range from the standard assumptions underlying the use of parametric analyses, to those specific to prepulse inhibition, e.g. related to the potential confounding effects of drug or diagnosis effects on startle magnitude. Data were demonstrated to be normally distributed and drug effects on PPI were shown to be independent of changes in startle magnitude. Analyses confirmed the hypothesis for the 20 mg dose of MEM in SZ patients.

The operational measure of mismatch negativity (MMN) is mean amplitude in response to oddball stimuli over the 135-205 ms range. The primary hypothesis was tested by an ANOVA of MMN with MEM dose as a within subject factor. The hypothesis that MEM will increase MMN in SZ patients was to be confirmed by a significant main effect of drug (active > PBO) or significant interaction among the variables of drug, dose (10 or 20 mg), diagnosis (healthy subject (HS) or SZ), and informative post-hoc comparisons. The assumptions behind these analyses range from the standard assumptions underlying the use of parametric analyses. Data were demonstrated to be normally distributed. Analyses confirmed the hypothesis for the 20 mg dose of MEM in SZ patients.

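### The PPI success rule has two routes to confirmation in each of two dose groups with no control across them, so a false confirmation in at least one dose group has a chance of about 5.5-10.5%

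*Protocol*

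**What the plan says.** Protocol section 9, part j (Statistics), sets the general rule: "Following a significant ANOVA, specific comparisons are made using Tukey's tests. Alpha is 0.05". No family-wise level is given.

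Under Power considerations, the PPI analysis in patients is a two-way repeated-measures ANOVA with drug and prepulse interval as within-subject factors. The hypothesis "will be confirmed by a significant effect of dose (active > PBO) or significant dose x interval (int) interaction and post-hoc comparisons". A favourable comparison may fall anywhere, since the text asks for "post-hoc comparisons at one or more prepulse intervals". The same paragraph records a "strong *a priori* prediction that the 120 ms prepulse interval will be most sensitive to PPI-enhancing effects of MEM", but does not make that interval the test.

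The sentence "All analyses will be conducted independently for each dose group" closes the genotype paragraph, though its wording covers every analysis. There are two dose groups of 30 patients, 10 mg and 20 mg, each with its own placebo day.

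The SAP supplies the number of intervals: "MEM dose and prepulse interval (10, 20, 30, 60 or 120 ms) as within subject factors". It then accepts a "significant main effect of drug (active > PBO) or significant interaction among the variables of drug, dose (10 or 20 mg", and the list goes on to diagnosis and prepulse interval. The accompanying post-hoc comparisons need only be informative, and no correction is named. The SAP reports the hypothesis confirmed at 20 mg, without saying by which route or at which interval.

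**The concern.** A rule that can be met in more than one way has a larger error rate than any one of its tests. Here a dose group can succeed by its main effect or by its interaction, and there are two dose groups. Nothing in either document says how the 0.05 is shared among these or in what order they are tested.

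The primary conclusion rests on this rule. Confirmation in one of two dose groups, which is what the SAP reports, is the case that the rule leaves uncontrolled. Without the route and the interval, a reader cannot attach an error rate to the result.

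**Working it through.** **Inputs.** Alpha 0.05, the two routes and 30 patients per dose come from protocol section 9.j, as does the separate analysis of two doses. The five intervals come from the SAP. Assumed, because the documents are silent: F tests at 0.05 counted as success only when active exceeds placebo, independent dose groups, and between-interval correlations of the active-minus-placebo differences from 0 to 0.9.

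**The plan's own figures.** The documents give no error rate for the whole rule. They give power of 0.92 (n=30) and 0.85 (n=24) at d=0.91. A two-sided two-sample t calculation returns 0.934 and 0.870, within two points of both. A paired calculation, if d is on the difference scale, returns 0.998 and 0.989. Either way, the stated power refers to one test, not to the either/or rule.

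**Step 1: one directional test.** A two-sided 0.05 test counted only when active exceeds placebo has a false-confirmation rate of 0.05/2 = 2.5%. Over two independent dose groups this is 1 - 0.975² = 4.9%.

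**Step 2: add the interaction route.** Null simulations of five-interval difference scores, with the favourable direction and a favourable post-hoc required, give for example (n=30, AR(1) correlation 0.6, uncorrected F):

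| Post-hoc reading | Main effect | Interaction and post-hoc | Either route, one dose | At least one dose |
|---|---|---|---|---|
| Unadjusted paired t | 2.5% | 2.2% | 4.5% | 8.9% |
| Tukey over all 10 cells | 2.6% | 1.1% | 3.5% | 7.0% |
| Bonferroni over 5 | 2.4% | 0.7% | 3.0% | 5.9% |

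The last column is 1 - (1 - p)², for example 1 - 0.9547² = 8.9%. The post-hoc reading matters because the protocol does not say over which family Tukey's test is run. With two drug levels at a single interval it is an unadjusted paired test. Over all 10 drug-by-interval cells it allows for 10 × 9 / 2 = 45 comparisons, and the critical t rises from 2.05 to 3.23.

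**Step 3: range over correlations.** From 0 to 0.9, one dose group runs from 2.8% to 5.4%. At least one of two dose groups then runs from 1 - 0.972² = 5.5% to 1 - 0.946² = 10.5%.

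**Step 4: the SAP rule.** With drug, dose, diagnosis and interval in the model, eight terms contain drug: the main effect, three two-way, three three-way and one four-way interaction. Treated as independent, at least one is significant with probability 1 - 0.95⁸ = 33.7%. That is not the confirmation rate, because post-hoc comparisons are also needed. Requiring a favourable one in the patients brings it to 9.7-13.4% if unadjusted, and to 3.4-4.2% with Bonferroni over 12 (assuming 30 subjects per diagnosis-by-dose cell). The SAP does not say which applies.

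**Step 5: power of the two candidate primary tests (n=30).**

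| True effect | 120 ms paired contrast | Existing rule, all-cells Tukey |
|---|---|---|
| dz=0.6 at 120 ms only | 0.89 | 0.69 (AR 0.5) to 0.82 (AR 0.7) |
| dz=0.4 at all five intervals (AR 0.5) | 0.57 | 0.89 |

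**The case against.** A reader might infer that five intervals give five further chances, or that the false-confirmation rate is near 20%. The documents do not support either. In the protocol the post-hoc comparisons are joined to a significant interaction and follow only after it, so they narrow that route. A rate of about 18.5% (1 - 0.95⁴), or 19-23% in simulation, arises only if direction and post-hocs are both ignored. Yet the protocol writes the direction into the main effect, and the hypothesis is that PPI increases. No direction is written beside the interaction, but a post-hoc showing lower PPI on memantine could not confirm an increase.

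It can also be said that each dose group, taken alone, stays at about 5% or less, that 0.05 is a per-test level with no family-wise promise, and that separate dose cohorts in a single-dose mechanistic study may be read as separate questions. The SAP's dose-specific wording fits that reading. The first of these stands: within one dose group the excess is over the 2.5% directional rate, not over 5%. The others weaken the point without removing it. Neither document says that the doses are separate claims, and the second route raises the rate within each dose even if they are.

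Nor does the rule generally cost power. It loses to the 120 ms contrast only when the effect is concentrated there. The protocol predicts that 120 ms will be the most sensitive interval, not the only one.

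**Conclusion.** The concern holds at a moderate size. The rule is uncontrolled across routes and doses: about 3-5% in one dose group and about 5.5-10.5% in at least one of two, against 2.5% for one directional test or 5% two-sided. Two doses alone take 2.5% to 4.9%; the interaction route accounts for the rest. The range depends on the assumed correlations and on how Tukey's test is read, and it covers PPI only.

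The SAP wording is the looser of the two. It admits interactions with dose and diagnosis, leaves the post-hoc comparisons undefined and names no correction. This does not show that the reported 20 mg result is false. It shows that its error rate cannot be stated from what is written.

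**What to change.** - Name one primary PPI test within the schizophrenia patients, direction active above placebo: either the drug main effect over intervals or, following the protocol's own prediction, the paired 120 ms contrast.
- Test 20 mg first at two-sided 0.05, since the protocol's effect size rests on that dose, and 10 mg only if 20 mg succeeds. Alternatively, split alpha as 0.025 + 0.025. At d=0.91 the split gives power of 0.886 (n=30) and 0.795 (n=24) by the two-sample calculation, or 0.994 and 0.975 by the paired one.
- Report the other route, the remaining intervals (Holm-adjusted paired tests) and the dose and diagnosis interactions as secondary or exploratory.
- Because the SAP was written with results in hand, state which route and interval confirmed the 20 mg finding, report the existing data against the chosen test, and say that the ordering was set afterwards. This makes the claim readable but cannot restore prospective error control.

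The cost is SAP wording and one re-analysis. The choice of test is a real trade-off: the 120 ms contrast gains power if the effect is concentrated there and loses it if the effect is spread over intervals. Naming either one removes the multiplicity between routes.
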